### **7.2.6 Assessment of Adverse Events**

All AEs and SAEs whether volunteered by the subject, discovered by study personnel during questioning, or detected through physical examination, laboratory test, or other means will be reported appropriately. Each reported AE or SAE will be described by its duration (i.e., start and end dates), regulatory seriousness criteria if applicable, suspected relationship to atezolizumab and/or abemaciclib, and actions taken.

• **Attribution** of the AE:

- Definite – The AE is *clearly related* to the study treatment.
- Probable – The AE is *likely related* to the study treatment.
- Possible – The AE *may be related* to the study treatment.
- Unlikely – The AE is *doubtfully related* to the study treatment.
- Unrelated – The AE is *clearly NOT related* to the study treatment.

To ensure consistency of AE and SAE causality assessments, investigators should apply the following general guideline:

**Yes:** Related (definite, probable, possible)

There is a plausible temporal relationship between the onset of the AE and administration of the atezolizumab and/or abemaciclib and the AE cannot be readily explained by the subject's clinical state, intercurrent illness, or concomitant therapies; and/or the AE follows a known pattern of response to the atezolizumab and/or abemaciclib or with similar treatments; and/or the AE abates or resolves upon discontinuation of the atezolizumab and/or abemaciclib or dose reduction and, if applicable, reappears upon re- challenge.

**No:** Not Related (unlikely, unrelated)

Evidence exists that the AE has an etiology other than the atezolizumab and/or abemaciclib (e.g., preexisting medical condition, underlying disease, intercurrent illness, or concomitant medication); and/or the AE has no plausible temporal relationship to atezolizumab and/or abemaciclib administration (e.g., cancer diagnosed 2 days after first dose of study drug).

Expected adverse events are those adverse events that are listed or characterized in the Package Insert (P.I) or current Investigator Brochure (I.B).

Unexpected adverse events are those not listed in the P.I or current I.B or not identified. This includes adverse events for which the specificity or severity is not consistent with the description in the P.I. or I.B. For example, under this definition, hepatic necrosis would be unexpected if the P.I. or I.B. only referred to elevated hepatic enzymes or hepatitis.

For patients receiving combination therapy, causality will be assessed individually for each protocol-mandated therapy.

## **7.2.7 Procedures For Eliciting, Recording, And Reporting Adverse Events**

### **7.2.7.1 Eliciting Adverse Events**

A consistent methodology for eliciting AEs at all subject evaluation time points should be adopted. Examples of non-directive questions include:

- “How have you felt since your last clinical visit?”
- “Have you had any new or changed health problems since you were last here?”

### **7.2.7.2 Specific Instructions for Recording Adverse Events**

Investigators should use correct medical terminology/concepts when reporting AEs or SAEs. Avoid colloquialisms and abbreviations.

#### *Infusion-Related Reactions and Cytokine-Release Syndrome*

There may be significant overlap in signs and symptoms of IRRs and cytokine-release syndrome (CRS). While IRRs occur during or within 24 hours after treatment administration, time to onset of CRS may vary. Differential diagnosis should be applied, particularly for late-onset CRS (occurring more than 24 hours after treatment administration), to rule out other etiologies such as delayed hypersensitivity reactions, sepsis or infections, HLH, tumor lysis syndrome, early disease progression, or other manifestations of systemic inflammation.

Adverse events that occur during or within 24 hours after study treatment administration and are judged to be related to study treatment infusion should be captured on the Adverse Event eCRF as a diagnosis (e.g., "infusion-related reaction" or "cytokine release syndrome"). Avoid ambiguous terms such as "systemic reaction." Cases of late-onset CRS should be reported as "cytokine-release syndrome" on the Adverse Event eCRF. Associated signs and symptoms of an IRR should be recorded on the dedicated Infusion-Related Reaction eCRF.

If a patient experiences both a local and systemic reaction to a single administration of study treatment, each reaction should be recorded separately on the Adverse Event eCRF, with associated signs and symptoms of an IRR also recorded separately on the dedicated Infusion-Related Reaction eCRF.

In recognition of the challenges in clinically distinguishing between IRRs and CRS, consolidated guidelines for medical management of IRRs and CRS are provided in Section 6.1 “Infusion-Related Reactions and Cytokine-Release Syndrome.”

### **7.2.7.3 Diagnosis vs. Signs and Symptoms**

If known at the time of reporting, a diagnosis should be reported rather than individual signs and symptoms (e.g., record only liver failure or hepatitis rather than jaundice, asterixis, and elevated transaminases). However, if a constellation of signs and/or symptoms cannot be medically characterized as a single diagnosis or syndrome at the time of reporting, it is acceptable to report the information that is currently available. If a diagnosis is subsequently established, it should be reported as follow-up information.

#### 7.2.7.4 Deaths

All deaths that occur during the protocol-specified AE reporting period (see Section 7.2.4), regardless of attribution, will be reported to the appropriate parties. When recording a death, the event or condition that caused or contributed to the fatal outcome should be reported as the single medical concept. If the cause of death is unknown and cannot be ascertained at the time of reporting, report “Unexplained Death”.

#### 7.2.7.5 Preexisting Medical Conditions

A preexisting medical condition is one that is present at the start of the study. Such conditions should be reported as medical and surgical history. A preexisting medical condition should be reassessed throughout the trial and reported as an AE or SAE only if the frequency, severity, or character of the condition worsens during the study. When reporting such events, it is important to convey the concept that the preexisting condition has changed by including applicable descriptors (e.g., “more frequent headaches”).

##### *Lack of Efficacy or Worsening of Underlying Cancer*

Deterioration that is judged by the investigator to have unexpectedly worsened in severity or frequency or changed in nature (i.e., deterioration beyond the expected pattern of progression of the underlying disease) should be recorded as an adverse event. When recording an unanticipated worsening of underlying cancer on the Adverse Event eCRF, it is important to convey the concept that the condition has changed by including applicable descriptors (e.g., “accelerated worsening of prostate cancer”). Events that are clearly consistent with the expected pattern of progression of the underlying disease should not be recorded as adverse events. These data will be captured as efficacy assessment data only. In most cases, the expected pattern of progression will be based on PCWG3 criteria. In rare cases, the determination of clinical progression will be based on symptomatic deterioration. However, every effort should be made to document progression through use of objective criteria. If there is any uncertainty as to whether an event is due to disease progression, it should be reported as an adverse event.

#### 7.2.7.6 Hospitalizations for Medical or Surgical Procedures

Any AE that results in hospitalization or prolonged hospitalization should be documented and reported as an SAE. If a subject is hospitalized to undergo a medical or surgical procedure as a result of an AE, the event responsible for the procedure, not the procedure itself, should be reported as the SAE. For example, if a subject is hospitalized to undergo coronary bypass surgery, record the heart condition that necessitated the bypass as the SAE.

Hospitalizations for the following reasons do not require reporting:

- Hospitalization or prolonged hospitalization for diagnostic or elective surgical procedures for preexisting conditions
- Hospitalization or prolonged hospitalization required to allow efficacy measurement for the study or
- Hospitalization or prolonged hospitalization for scheduled therapy of the target disease of

the study

#### **7.2.8 Adverse Event of Special Interest (AESI) for Atezolizumab**

AESIs are a subset of adverse events which may be of scientific and medical concern specific to the study drug, for which ongoing monitoring and expedited communication is required. Such an event might require further investigation in order to characterize and understand it. Depending on the nature of the event, rapid communication by the trial Sponsor to other parties (e.g., Regulatory Authorities) may also be warranted.

AESIs applicable to all participants in this trial are:

- Cases of potential drug-induced liver injury (DILI) that include an elevated ALT or AST in combination with either an elevated bilirubin or clinical jaundice, as defined by Hy's law:
  - Treatment-emergent ALT or AST  $> 3 \times$  ULN in combination with total bilirubin  $> 2 \times$  ULN
  - Treatment-emergent ALT or AST  $> 3 \times$  ULN in combination with clinical jaundice
- Suspected transmission of an infectious agent by the study drug (STIAMP), as defined below:  
Any organism, virus, or infectious particle (e.g., prion protein transmitting transmissible spongiform encephalopathy), pathogenic or non-pathogenic, is considered an infectious agent. A transmission of an infectious agent may be suspected from clinical symptoms or laboratory findings that indicate an infection in a patient exposed to a medicinal product. This term applies only when a contamination of the study drug is suspected.
- ILD/Pneumonitis

AESIs associated with participants receiving Atezolizumab:

- Systemic lupus erythematosus
- Events suggestive of hypersensitivity, infusion-related reactions, cytokine release syndrome, macrophage activating syndrome and hemophagocytic lymphohistiocytosis syndrome
- Nephritis
- Ocular toxicities (e.g., uveitis, retinitis, optic neuritis)
- Grade  $\geq 2$  cardiac disorders (e.g., atrial fibrillation, myocarditis, pericarditis)
- Vasculitis
- Autoimmune hemolytic anemia
- Severe cutaneous reactions (e.g., Stevens-Johnson syndrome, dermatitis bullous, toxic epidermal necrolysis)
- Myelitis
- Facial Paresis

#### **7.2.9 Other Special Situations**

The following other Special Situations Reports should be collected even in the absence of an Adverse Event and transmitted to Genentech:

- Data related to overdose, abuse, misuse or medication error (including potentially exposed or intercepted medication errors)
- In addition, reasonable attempts should be made to obtain and submit the age or age group of the patient, in order to be able to identify potential safety signals specific to a particular population

#### *Pregnancy*

Such events include pregnancy (occurring in the partner of the male study subject), where the fetus may have been exposed to the study drug (conception while the study subject was receiving protocol therapy or within 5 months after the last dose of study drug); data related to the Product usage during breastfeeding; study drug interaction; study drug overdose, abuse or misuse; or medication error (including potentially exposed or intercepted medication errors). In addition, reasonable attempts should be made to obtain and submit the age or age group of the patient, in order to be able to identify potential safety signals specific to a particular population

NOTE: Abortions, whether accidental, therapeutic, or spontaneous, should always be classified as serious, and reported as an SAE. Similarly, any congenital anomaly/birth defect in a child born to a female subject exposed to the study drug should be reported as an SAE.

#### **7.2.10 Product complaints**

A Product Complaint is defined as any written or oral information received from a complainant that alleges deficiencies related to identity, quality, safety, strength, purity, reliability, durability, effectiveness, or performance of a product after it has been released and distributed to the commercial market or clinical trial.

#### **7.2.11 Post-Study Adverse Events**

The investigator should expeditiously report any SAE occurring after a subject has completed or discontinued study participation if attributed to prior atezolizumab and/or abemaciclib exposure. If the investigator should become aware of the development of cancer or a congenital anomaly in a subsequently conceived offspring of a female subject [including pregnancy occurring in the partner of a male study subject] who participated in the study, this should be reported as an SAE adequately to Genentech drug Safety during follow up period.

### **7.3 Dose-Limiting Toxicities (DLT)**

A DLT will be defined as any of the following treatment-related events at any point during drug dosing:

#### Hematologic Toxicity

- Grade 3 thrombocytopenia associated with clinically significant bleeding and requiring platelet transfusion

- Grade 4 thrombocytopenia
- Grade  $\geq 3$  febrile neutropenia
- Grade  $\geq 3$  anemia requiring a blood transfusion
- Other Grade 4 toxicity lasting  $>7$  days

#### Non-Hematologic Toxicity

- Grade  $\geq 3$  fatigue lasting  $>7$  days
- Grade  $\geq 3$  nausea, vomiting, and diarrhea lasting  $>3$  days despite optimal medical management
- Grade  $\geq 3$  hypertension despite maximal medical therapy
- Grade 2 pneumonitis that does not resolve to Grade  $\leq 1$  within 14 days after initiation of optimal medical management including corticosteroid therapy
- Grade  $\geq 3$  colitis or noninfectious pneumonitis
- Grade 3 irAE\* (excluding colitis or pneumonitis) that:
  - does not downgrade to Grade 2 within 14 days after onset of the event despite optimal medical management  
or
  - does not downgrade to Grade  $\leq 1$  or the patient's baseline level within 30 days of event onset
- Grade 4 irAE\*

#### Other Toxicity

- ALT or AST:
  - $>8 \times$  ULN, if the patient does not have HCC or liver metastasis  
or
  - $\geq 2$ -fold above the patient's baseline value that lasts  $>7$  days, if the patient has HCC or liver metastasis and had ALT or AST  $>3.0 \times$  ULN at baseline  
or
  - $>3 \times$  ULN with concomitant bilirubin  $>2 \times$  ULN, in the absence of cholestasis
- Grade 3 bilirubin (total) level
- Grade 3 or 4 amylase or lipase that does not resolve to Grade  $\leq 2$  within 7 days of starting IV corticosteroid therapy
- Other Grade 3 or 4 laboratory value lasting  $>14$  days or requiring medical intervention
- Grade 5 toxicity (i.e. event that results in death)
- Toxicity otherwise deemed by the treating and/or Sponsor Investigator to be dose limiting (e.g., toxicity that is possibly related to study treatment and requires treatment discontinuation prior to completion of Cycle 1; persistent Grade  $>2$  toxicities causing a delay of  $>14$  days in initiating Cycle 2)

\*irAE=immune-related Adverse Event (i.e. an Adverse Event consistent with an immune-mediated mechanism of action with no clear alternate etiology)

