Adverse effects of the combination in I3Y-MC-JPCE were similar to what would be expected for the single agents, except for a higher than expected rate of grade 3 or higher elevations in liver function tests (LFTs), which were reversible upon discontinuation, and interstitial lung disease (ILD)/pneumonitis events. Grade 3 or higher increase of alanine aminotransferase (ALT) was seen in 24% of patients in Arm A, 0% in Arm B, 11% in Arm C, and 31% in Arm D; grade 3 or higher ILD/pneumonitis was seen in 3 patients in Arm A, 1 patient in Arm B, not reported for Arm C, and 2 patients in Arm D who subsequently died as a result of pneumonitis.

There are key differences in patient population and choice of CPI between I3Y-MC-JPCE and the current trial. A recent meta-analysis reported the incidence of grade  $\geq 3$  adverse events to be greater for anti-PD-1 agents compared to anti-PD-L1 agents (OR 1.58; 95% CI 1.00-2.54) (54). In similar patient populations (understanding the limitations of cross-trial comparisons), incidence of grade  $\geq 3$  pneumonitis appeared to be numerically higher with anti-PD-1 agents in trials of monotherapy in urothelial carcinoma (2.3% for pembrolizumab in KEYNOTE-045 (55), none reported for atezolizumab in IMvigor211 (56)) and in PD-L1+ NSCLC (2.6% for pembrolizumab in KEYNOTE-010 (57), 1% for avelumab in JAVELIN Lung 200 (58)), and in

combination trials with chemotherapy in non-squamous NSCLC (3% for pembrolizumab in KEYNOTE-189 (59), 2% for atezolizumab in IMpower132 (60)) and in squamous NSCLC (2.5% for pembrolizumab in KEYNOTE-407 (61), 1% for atezolizumab in IMpower131 (62)). Safety data of the combination of abemaciclib with an anti-PD-L1 CPI (such as atezolizumab, avelumab or durvalumab) has yet to be reported.

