  - platelets  $\geq 100,000/\text{mcL}$  (without transfusion or growth factor in prior 28 days)
  - Serum albumin  $\geq 25 \text{ g/L}$  (2.5 g/dL)
  - total bilirubin  $\leq 1.5 \times$  institutional upper limit of normal, unless the subject has known or suspected Gilbert's syndrome in which case total bilirubin must be  $\leq 2 \times$  ULN
  - AST(SGOT)/ALT(SGPT)  $\leq 1.5 \times$  institutional upper limit of normal, except for patients assigned to atezolizumab monotherapy in Arm C for whom  $\leq 2.5 \times$  upper limit of normal is permitted
  - INR and aPTT  $\leq 1.5 \times$  institutional upper limit of normal, unless the subject is receiving therapeutic anticoagulation, in which case they must be on a stable anticoagulant regimen
  - creatinine clearance  $\geq 30 \text{ mL/min}/1.73 \text{ m}^2$  (by Cockcroft-Gault formula or 24-hour urine collection)

- 3.1.10 Life expectancy of at least 6 months, as determined by a study Investigator.
- 3.1.11 Ability to swallow oral medications.
- 3.1.12 Ability to understand and willingness to sign an IRB-approved informed consent.

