## 5.2. Pre-Treatment Criteria

Pre-treatment assessments should be performed within 72 hours of planned treatment dose. Results from the patient's complete blood counts and serum chemistry must be reviewed prior to drug dosing. Study agents must be dispensed or administered only to subjects enrolled in the study and in accordance with the protocol. Standard institutional procedures for administering an oral agent via by mouth will be followed. An adequate supply will be provided with instructions on home administration.

### 5.2.1. Cycle 1, Day 1

The patient's laboratory parameters must meet eligibility criteria (section 3.1.9) to initiate cycle 1 day 1 of trial therapy. Transfusion or growth factors are not permitted between screening up to and including cycle 1 day 1 to re-meet eligibility criteria except for

patients assigned to atezolizumab monotherapy in Arm C for whom red blood cell transfusion to meet eligibility criterion for hemoglobin is permitted.

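### The ALT/AST dose-limiting-toxicity criterion for patients with liver metastases needs a baseline that eligibility forbids, so an isolated transaminase rise in these patients meets no explicit ALT/AST criterion

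*Combined protocol and SAP*

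**What the plan says.** Section 7.3 (Other Toxicity) lists three alternative ALT/AST criteria:

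1. A value above 8 × ULN, "if the patient does not have HCC or liver metastasis".
2. A value at least 2-fold above the patient's baseline for more than 7 days, "if the patient has HCC or liver metastasis and had ALT or AST" above 3.0 × ULN at baseline.
3. A value above 3 × ULN "with concomitant bilirubin" above 2 × ULN, without cholestasis.

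Section 3.1.9 sets the entry ceiling for AST and ALT at 1.5 times the "institutional upper limit of normal, except for patients assigned to atezolizumab monotherapy in Arm C for whom" the ceiling is 2.5 × ULN. It makes no allowance for liver metastases. Section 5.2.1 applies the limits again before the first dose: "The patient's laboratory parameters must meet eligibility criteria (section 3.1.9) to initiate cycle 1 day 1 of trial therapy".

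Liver metastases are not an exclusion in Section 3.3. Section 11.2.2 lists liver among the visceral sites to be assessed, and Section 9.1.2 names it as a possible biopsy site.

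Section 13.1.1 names a primary dose-safety endpoint for the abemaciclib cohort of Arm C and refers to Section 7.3 for its definition. Section 13.3 summarises safety for abemaciclib monotherapy and for the combination by the Section 7.3 DLT rate with a 90% confidence interval, alongside adverse events by incidence and grade.

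**The concern.** The second criterion is the only one written for an isolated transaminase rise in a patient with liver metastases, and its entry condition conflicts with the trial's own eligibility limits. The first criterion is closed to the same patients by its wording.

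A DLT rate is interpretable only if the same event is scored the same way in every patient, or differently by a rule that can operate. Here one group has an automatic threshold and the other has none. If hepatic events occur in patients with liver metastases, the reported rate may be too low, by an amount that depends on the site mix of the cohort and on individual judgement. The protocol treats liver toxicity as a live issue: Section 2.3.3 describes the side effects of abemaciclib with an anti-PD-1 antibody as similar to those of the single agents "except for a higher than expected rate of grade 3 or higher elevations in liver function tests (LFTs").

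**Working it through.** The plan states no figure to reproduce. The check sets the passages side by side and follows one event through them.

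**Step 1: can criterion 2 be reached?**

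| Group | Highest ALT/AST allowed at entry and at cycle 1 day 1 (3.1.9, 5.2.1) | Baseline that criterion 2 requires (7.3) | Reachable? |
|---|---|---|---|
| Arm A, Arm B, Arm C abemaciclib | 1.5 × ULN | > 3.0 × ULN | No |
| Arm C atezolizumab monotherapy | 2.5 × ULN | > 3.0 × ULN | No |

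The required baseline is more than 3.0 / 1.5 = 2 times the ceiling in the abemaciclib groups. Appendix B-3.7 permits no eligibility exception without IRB approval, so no patient who meets the criteria as written can satisfy criterion 2.

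**Step 2: the same event in two patients.** Take a baseline at the cap (1.5 × ULN), a peak of 15 × ULN, bilirubin not above 2 × ULN, and a duration between 7 and 14 days. The rise is 15 / 1.5 = 10-fold over baseline, which is Grade 3 in Table 22 (above 5.0 and up to 20.0 times an abnormal baseline).

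| Criterion | No liver metastases | Liver metastases |
|---|---|---|
| 1: > 8 × ULN | Met (15 > 8) | Does not apply |
| 2: ≥ 2-fold for > 7 days, baseline > 3.0 × ULN | Does not apply | Size and duration met; fails on baseline (1.5) |
| 3: bilirubin > 2 × ULN | Not met | Not met |
| Result on ALT/AST criteria | DLT | No criterion met |

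The peak plays no part in the right-hand column. A rise to 25 × ULN with bilirubin not above 2 × ULN gives the same result.

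**Step 3: what else in Section 7.3 could count it?**

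- *Other Grade 3 or 4 laboratory value.* It must last more than 14 days or require medical intervention, and 'Other', coming after a dedicated ALT/AST item, must be read to include ALT/AST. Criterion 1 carries no such conditions.
- *Immune-related events.* These need an immune-consistent mechanism with no clear alternative cause. A Grade 3 event must also fail to downgrade within 14 or 30 days. This fits poorly with direct toxicity of abemaciclib given alone.
- *Other Grade 4 toxicity lasting more than 7 days.* This is listed under hematologic toxicity.
- *Toxicity deemed dose limiting by the treating or sponsor investigator.* This is open, but it is a judgement.

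**Step 4: how many patients fall under the gap?** The documents do not say. As an assumption only, if 10% to 25% of the 27 + 16 = 43 planned abemaciclib monotherapy patients have liver metastases, then 0.10 × 43 = 4.3 to 0.25 × 43 = 10.8, or about 4 to 11 patients. Within the 16 in Arm C the range is 1.6 to 4. These are patients without a reachable criterion for an isolated rise, not missed DLTs.

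**The case against.** The strongest reply is that the gap is narrow and little now depends on it. Much of that stands.

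- **Other routes exist.** A reader might infer that a transaminase rise in a patient with liver metastases can never be a DLT. The documents do not support that. The investigator-judgement item gives fairly concrete examples: discontinuation before the end of cycle 1, and persistent toxicity above Grade 2 delaying cycle 2 by more than 14 days. Table 22 suspends abemaciclib for Grade 3 and discontinues it for Grade 4 regardless of liver metastases, so severe early rises may reach those examples. Table 17 prescribes corticosteroids for Grade 3 or 4 hepatic events under atezolizumab, which would satisfy the intervention condition. The clearest loss is the short-lived isolated rise. These routes remain conditional or subjective and do not replace an automatic threshold.
- **No enrolment rule now depends on it.** Section 13.3 records that combination enrolment was halted outside the Bayesian plan. Adverse events are reported by grade for every treated patient, so the rise stays visible. Table 22 dose management does not use the DLT definition. What remains affected is the reported DLT rate and the endpoint built on it.
- **A large effect cannot be shown.** Section 2.3.3 gives Grade 3 or higher ALT increases of 24%, 0%, 11% and 31% in four cohorts, and a reader might apply these here. They come from abemaciclib with pembrolizumab, one cohort also with anastrozole. They use a lower threshold than 8 × ULN and are not restricted to isolated rises. Nor do the documents support an example in which two missed events turn 2/16 (90% CI 2.3–34.4%) into 0/16 (0–17.1%). With at most 4 exposed patients in Arm C, that means half or more of them. Even at the borrowed 31%, the chance of two or more among 4 is 1 − 0.69⁴ − 4 × 0.31 × 0.69³ ≈ 37%; at 11% it is about 6%.
- **Hepatic reserve.** A reader might suppose that these patients enter with the poorest liver function. Section 3.1.9 applies the same transaminase, bilirubin, albumin and INR limits to everyone.

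**Conclusion.** The contradiction is in the text and needs no outside source. Criterion 2 applies to no eligible patient, and neither of the other two ALT/AST criteria captures an isolated rise in a patient with liver metastases. Because Section 7.3 defines both the Section 13.1.1 dose-safety endpoint and the Section 13.3 DLT rate, this is an error in a stated endpoint rule rather than a missing detail.

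The direction is towards under-counting hepatic DLTs in one subgroup. The size is unknown: it depends on the share with liver metastases, the frequency of isolated rises on abemaciclib alone, and how often the remaining routes catch them. None of these is in the documents. The conclusion assumes that the eligibility limits are observed and that baseline means a value at screening or cycle 1 day 1.

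**What to change.** Reconcile the Section 7.3 ALT/AST criteria with Sections 3.1.9 and 5.2.1 so that every eligible patient, with or without liver metastases, has a reachable ALT/AST criterion. The threshold, and whether it should differ by liver involvement, is for the sponsor to decide. State also whether the item on other Grade 3 or 4 laboratory values covers ALT and AST.

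Do this before any DLT rate is reported. Then score patients from the chemistry panels already collected each cycle. For patients already treated, including the 8 in Arm B, show the DLT count under both the current and the reconciled definitions and label the change, since it is made after open-label data exist.

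The cost is a short protocol wording change and a re-score of existing laboratory data, with no new assessments. The downside is that the reported DLT rate may rise slightly.
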